### 4.1.2. Baseline Definition

For all endpoints (except as noted in baseline definitions), the baseline value will be the latest pre-dose of GSK3745417 assessment with a non-missing value, including those from unscheduled visits, if available. If time is not collected, Day 1 assessments are assumed to be taken prior to first dose and used as baseline.

For laboratory data, baseline will be the latest non-missing pre-dose value.

For ECG analyses, if the latest, non-missing pre-dose values is from triplicate, the subject level baseline is defined as the mean of triplicate baseline assessments.

Unless otherwise stated, if baseline data are missing, no derivation will be performed, and baseline will be set to missing.

# 4.2. Primary Endpoint(s) Analyses

### 4.2.1. Definition of endpoint(s)

An AE is considered a DLT if it is considered by the investigator to be clinically relevant and attributed (definitely, probably, or possibly) to the study intervention and meets at least 1 of the criteria listed in Table 7 of the protocol. If an AE is considered related to the underlying disease, it is not a DLT. The DLT period is 28 days starting at Day 1 of each cycle. The analysis of DLTs will be based on the DLT-Evaluable Analysis Set, unless otherwise specified.

The definitions of an AE or Serious Adverse Event (SAE) can be found in Appendix 3 of the protocol. AEs will be reported by the participant (or, when appropriate, by a caregiver, surrogate, or the participant's legally authorized representative). The analysis of AEs and SAEs will be based on the Safety Analysis Set, unless otherwise specified.

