# **Overall Design and Brief Summary:**

This is a Phase 1, open label, dose escalation study to evaluate safety, pharmacokinetics, and pharmacodynamics of intravenous GSK3745417 in participants with relapsed or refractory AML or high risk MDS.

The study will be conducted in a staged approach consisting of 2 parts. Part 1 will evaluate a dosing schedule of a 5 days on/2 days off schedule for 2 weeks, and then have an additional 2 weeks off dose for observation for a total of 28 days in each cycle (5/2)/5q28d). Once a maximum tolerated dose (MTD) has been established, additional cohorts may be opened to refine dosing frequency optimization. Each cohort will include at least 3 participants and dosing of participants entering the study will be staggered by at least 5 days from D1 of previous patient for the first cohort only. Part 1 will include intra-patient dose escalation for 3 cycles, according to safety and tolerability parameters. The starting dose for Cycle 1 will be escalated in the next dose-escalation cohort until a cohort level starting dose-based MTD is reached. Individual patients may titrate above the starting dose-based MTD based on tolerability. Dose escalation cohorts will start with Cycle 1 at 12.5 µg GSK3745417. Within a cohort for an individual subject the dose may double for Cycle 2, and double again for Cycle 3 based on individual tolerability. The starting dose of subsequent cohorts will increase by 2-fold from Cycle 1 of the previous cohort. Patients may be dose reduced for subsequent cycles if there is lack of tolerability in the previous cycle (Section 6.4). The DLT period will be 28 days starting at Day 1 of Cycle 1 of each cohort. After 3 induction cycles, if a complete response (CR) or partial

response (PR) (IWG) is observed (See Appendix 9) each patient will continue with maintenance weekly dosing at the Cycle 3 dose level until disease progression or unacceptable toxicity. Participants with progressive disease after 3 induction cycles will be withdrawn from study. Participants with stable disease or PR after 3 cycles might receive additional cycles if the assessment by the investigator determined a benefit and GSK Medical Monitor agrees.

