### Part 1

Part 1 will evaluate a dosing schedule of a 5 days on/2 days off schedule for 2 weeks, and then have an additional 2 weeks off dose for observation for a total of 28 days in each cycle (5/2/5 q28d). Once an MTD has been established, additional cohorts may be opened to refine dosing frequency optimization. Each cohort will include at least

3 participants. Part 1 will include intra-patient dose escalation for 3 cycles, according to safety and tolerability parameters. The starting dose for Cycle 1 will be escalated in the next dose escalation cohort until a cohort level MTD is reached. The first participant at the starting dose level(s) of each cohort will begin treatment after review of safety data and DEM to allow assessment of initial safety data before beginning the next participant's treatment. The dosing of subsequent participants will be staggered by  $\geq 5$  days.

Day	-1	1	2	3	4	5	6	7	8	9	10	11	12	13	14-28
GSK3745417		Х	Х	Х	Х	Х			Х	Х	Х	Х	Х		
In-patient	Х	Х	Х	Х	Х	Х	Х	Х	Х	Х	Х	Х	Х	Х	
Non-azole antifungal	Х	Х	Х	Х	Х	Х	Х	Х	Х	Х	Х	Х	Х	Х	Х

Table 6	Dosing and Hospitalization Schedule for Cycles 1 - 3

Dose escalation will initiate with Cycle 1 at 12.5 µg GSK3745417 as the first cohort and the Cycle 1 dose will increase by 2-fold between cycles (3 dose levels). The starting dose of subsequent cohorts will increase by 2-fold from Cycle 1 of the previous cohort. Patients may be dose reduced for subsequent cycles if there is lack of tolerability in the previous cycle (Section 6.4). The DLT period will be 28 days starting at Day 1 of Cycle 1 of each cohort. After 3 induction cycles, if a CR or PR (IWG) is observed (See Appendix 9), each patient will continue with maintenance weekly dosing at the Cycle 3 dose level until disease progression or unacceptable toxicity. Participants with progressive disease after 3 induction cycles will be withdrawn from study. Participants with stable disease or PR after 3 cycles might receive additional cycles if the assessment by the investigator determined a benefit and GSK Medical Monitor agrees.

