### **Dose Escalation**

To complete dose escalation in Part 1, it is estimated that up to 22 participants will be enrolled. Dose escalation for Part 1 will use the N-CRM. This method utilizes a 2parameter logistic model, with parameters  $\alpha$  and  $\beta$ , to describe the relationship between DLT and dose (12.5, 25, 50, 100, 200 µg). The N-CRM estimates, for each potential dose, the posterior probabilities that the DLT rate lies in each of 4 toxicity intervals:

- [0%,16%)=Underdosing range;
- [16%,33%)=Target toxicity range;
- [33%,50%)=Excessive toxicity range;
- [50%,100%)=Unacceptable toxicity range.

Additionally, the following constraints for the recommended dose will be maintained:

The posterior probability of the DLT rate lying in the Excessive Toxicity or Unacceptable Toxicity range is less than 25%.

Dose escalation will continue until:

i. An MTD is found:

At least 9 participants have been treated at the current target dose

AND

The posterior probability that the DLT rate for the current dose lies in either the excessive toxicity or unacceptable toxicity range is less than 25%.

AND

The posterior probability that the DLT rate for the next higher dose lies in either the excessive toxicity or unacceptable toxicity range is greater than or equal to 25%.

OR

ii. The RP2D has been reached and at least 9 participants have been dosed at that dose level.

OR

iii. All doses have a posterior probability of lying in either the excessive toxicity or unacceptable toxicity range of greater than or equal to 25%

AND

At least 2 DLTs have been observed.

All available data, including safety, PK, and pharmacodynamic data from current and prior cohorts will be reviewed at dose escalation meetings after each cohort in Part 1. Clinical judgment by the Medical Monitor, recommendation from GSK clinical pharmacologist, GSK scientist and GSK statistician, and in consultation with the investigators can decide dose escalation or reduce the recommended dose as deemed appropriate at any time during the trial.

**Maximum Tolerated Dose:** The MTD will be defined as the dose within cycle that has the highest probability of having a DLT rate within the target toxicity interval, and for which the probability that the DLT rate lies within the excessive toxicity, or the unacceptable toxicity window is less than 25%. The DLT observation period will be 28 days.

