# 4.1.1. Dose Limiting Toxicities (DLT)

All toxicities will be graded using National Cancer Institute – Common Toxicity Criteria for AEs (NCI-CTCAE), version 5.0.

An AE is considered to be a DLT if it is considered by the investigator to be clinically relevant and attributed (definitely, probably, or possibly) to the study intervention and meets at least 1 of the criteria listed in the table below. If an AE is considered related to the underlying disease it is not a DLT. The DLT period is 28 -days starting at Day 1 of each cycle. Participants unable to receive at least 70% of scheduled doses within the DLT

period for reasons other than toxicity (e.g., acute illness, disease progression) will not be considered evaluable.

Toxicity	DLT Definition			
Cytokine Release Syndrome (CRS)	Grade 3 or 4 (See Section 10.4)			
TLS	Grade 3 or Grade 4 TLS (Cairo Bishop criteria, Appendix 11) that cannot be managed/ is not resolved within 72 hours			
Liver Toxicity	ALT $\geq$ 3x upper limit of normal (ULN), plus bilirubin $\geq$ 2x ULN (>35% direct) or plus international normalized ratio (INR)>1.5 (Possible Hy's law)			
Other	
 
Grade ≥3 non-hematologic toxicity of any duration with the following exceptions:
 
Transient (≤ 72 hours) abnormal laboratory value without associated clinically significant signs or symptoms
 
Individual parameters of CRS which collectively constitute <grade 3="" crs<="" li=""> 
Nausea, vomiting, or diarrhea that improves with supportive care within 72 hours
 
Alopecia of any grade
 
Grade 3 fatigue with duration <7 days
 
Grade 3 headache that resolves with supportive treatment to ≤Grade 2 within 24 hours
 
G3 acute renal injury considered related to TLS which improves or resolves with appropriate fluids and management of TLS
 
Grade ≥3 immune-related toxicity that does not resolve to Grade ≤1 or baseline within 8 days despite adequate immune suppressive therapy. Any other event which in the judgment of the investigator and GSK Medical Monitor is considered to be a DLT.
 </grade>

			

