## Figure 7 Dose Toxicity Scenarios (with dose strength shown in units of mg)

#### Mid-dose DLT

For each scenario, 10000 clinical trials were simulated. The average sample sizes over the 10000 clinical trials simulated under the three scenarios were 14, 20, 22, respectively.

Details of the simulation results are provided in Table 14. For the simulations, the selected reference dose was the median (0.05 mg).

Table 14	Summary of Simulation Results
----------	-------------------------------

Scenario	% of Trials Selecting Correct Dose(s) as MTD	% of Trials Selecting Underestimating MTD	% of Trials Selecting Overestimating MTD	Average Sample Size
Low-dose DLT	92.69%	-	2.88%	~14
Mid-dose DLT	85.72%	13.76%	0.52%	~20
High-dose DLT	87.01%	12.99%	-	~22

**Maximum Tolerated Dose:** The MTD will be defined as the dose that has the highest probability of having a DLT rate within the target toxicity interval, and for which the probability that the DLT rate lies within the excessive toxicity, or the unacceptable toxicity window is less than 25%. The DLT observation period will be 28 days.

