## 9.4.3.3. Exploratory Biomarker Analyses

## 9.5. Interim Analysis

The primary driver for the dose-escalation decision(s) will be safety and tolerability of each dose cohort. For Part 1 induction and Part 2 maintenance, dose escalation and de-escalation decisions will be guided by an N-CRM model and mTPI, respectively. Predicted DLT rates will be provided with the aim of escalating to doses with small probability of excessive or unacceptable toxicity. Preliminary safety and available PK/PD data will be reviewed by the GSK study team and investigators after completion of each dose cohort. This review will support the decision on the dose level in the next dose cohort.

After the last cohort of participants completes the DLT observation period for induction in Part 1, a formal interim analysis will be performed to support the initiation of Part 2 and the recommended dose level for induction. Data considered to support these decisions will include, but are not limited to, safety, PK profile, PD, and observed signs of clinical activity. Details of the interim analysis will be provided in the SAP.

For Part 2, assessment of efficacy and safety will be performed after the first futility assessment based upon a minimum of 13 participants with available unconfirmed overall response data, separately for the AML and HR-MDS cohorts. If the stopping criteria for futility are met in either the AML or MDS cohort, further enrollment in that cohort may be stopped.

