# 1. INTRODUCTION

The purpose of this SAP is to describe the planned analyses to be included in the Clinical Study Report (CSR) for Study 209809. Due to the termination of this study, only the planned Part 1 analyses described in the protocol will be produced for a synoptic CSR.

Additional details with regards to data handling conventions and the specification of data displays will be provided in the Output and Specification (OPS) document. Additional data will be available to view via RAPIDO DV (for more details see OPS).

[figure not shown]

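### SAP 4.2.1 starts the Part 1 DLT window at every cycle while the protocol's Part 1 text starts it at Cycle 1, so the by-cohort DLT table can include events at up to four times the cohort's starting dose

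*SAP*

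**What the plan says.** The current SAP was amended after the study was terminated. Its Introduction limits it to Part 1: "only the planned Part 1 analyses described in the protocol will be produced for a synoptic CSR". Section 4.2.1 defines the DLT window as "The DLT period is 28 days starting at Day 1 of each cycle". SAP 4.2.2 then plans a count of patients with DLTs in each cohort, and Protocol 9.4.2.2 likewise groups DLTs by dose cohort.

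The protocol gives two windows for Part 1. The synopsis (Overall Design) and Section 4.1 (Part 1) both say "The DLT period will be 28 days starting at Day 1 of Cycle 1 of each cohort". Section 4.1.1, which holds the DLT criteria, says "The DLT period is 28 -days starting at Day 1 of each cycle". The SAP follows 4.1.1.

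The dose is not constant across cycles. The synopsis says "Within a cohort for an individual subject the dose may double for Cycle 2, and double again for Cycle 3 based on individual tolerability". Each new cohort is defined by a Cycle 1 dose twice that of the cohort before.

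The DLT-evaluable set in SAP 3 requires follow-up for the DLT observation period. It removes participants who, for reasons other than toxicity, received less than 70% of planned doses in the DLT period. It names no cycle for either condition.

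**The concern.** DLT frequency is part of the Part 1 primary endpoint (SAP 1.1). With dose doubling inside a cohort, the window decides which dose a by-cohort DLT count describes. A Cycle 1 window gives the count at the starting dose. An each-cycle window mixes one, two and four times that dose under the starting-dose label.

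The SAP's other tables use a different rule. AE tables are by dose level (SAP 4.1.1), and an AE goes to the dose level in force when it first occurred (SAP 4.2.2). One Cycle 3 event in the first cohort could therefore appear at 50 µg in the AE tables and under the 12.5 µg cohort in the DLT summary.

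Two programmers, one following SAP 4.2.1 and one following Protocol 4.1, could produce different numerators and denominators for the same primary-endpoint table, each with a text to cite.

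**Working it through.** The plan gives no figure on this point to reproduce. The check sets the texts side by side and then sizes the difference.

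**1. The texts**

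| Place | Start of the 28-day window |
|---|---|
| Protocol synopsis, Overall Design; Protocol 4.1, Part 1 | Day 1 of Cycle 1 |
| Protocol 4.1.1; SAP 4.2.1 | Day 1 of each cycle |
| Protocol 4.1 (Dose Escalation) and 9.2, MTD definition | No cycle named: "The DLT observation period will be 28 days" |
| Protocol 9.5 | A single period that a cohort completes: "After the last cohort of participants completes the DLT observation period for induction in Part 1" |
| SAP 3, DLT-evaluable set | No cycle named |

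The two sections specific to Part 1 agree on Cycle 1. The references to one observation period per cohort fit that reading. Cycle 1 is therefore the likelier intent, but SAP 4.2.1 says otherwise and SAP 4.8 does not mention the point.

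**2. Dose and time at risk**

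For starting dose s, the Cycle 1/2/3 doses with full escalation are s, 2s and 4s. For the model doses this gives 12.5/25/50, 25/50/100, 50/100/200, 100/200/400 and 200/400/800 µg. Time at risk is 1 × 28 = 28 days or 3 × 28 = 84 days.

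**3. Effect on the reported proportion**

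Clopper–Pearson 95% limits for x of n: the lower limit is the 0.025 quantile of Beta(x, n−x+1) and the upper is the 0.975 quantile of Beta(x+1, n−x). For x = 0 the upper limit is 1 − 0.025^(1/n).

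| Hypothetical case | Cycle 1 window | Each-cycle window |
|---|---|---|
| n = 3, no Cycle 1 DLT, one Cycle 3 DLT at 50 µg | 0/3 (0–70.8%) | 1/3 (0.8–90.6%) |
| n = 9, one Cycle 1 DLT, one later | 1/9 = 11.1% (0.3–48.2%) | 2/9 = 22.2% (2.8–60.0%) |
| n = 9, two Cycle 1 DLTs, one later | 2/9 = 22.2% (2.8–60.0%) | 3/9 = 33.3% (7.5–70.1%) |

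Nine is the protocol's minimum before an MTD is declared ("At least 9 participants have been treated at the current target dose"). In the two n = 9 cases the observed proportion crosses the 16% or the 33% band limit in Protocol 4.1. These are raw proportions. The protocol applies the bands to posterior probabilities.

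**4. Effect on the denominator**

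Take a participant with 10/10 doses in Cycle 1 (100%) and 4/10 in Cycle 2 (40%) before progression. The 70% rule is met in Cycle 1 and failed in Cycle 2. A cohort of three with no DLT could then be reported as 0/3 (upper limit 70.8%) or 0/2 (upper limit 1 − 0.025^(1/2) = 84.2%).

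**5. Secondary: the dose-escalation model**

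Inputs are from Protocol 9.2: α mean −1.7907 (SD 1.6787), ln β mean 0.1961 (SD 0.1706), correlation −0.7729, reference dose 50 µg. I assumed the form logit p = α + β ln(dose/50) and integrated over a ±7 SD grid. The posterior probability that the DLT rate at 50 µg is 33% or more is:

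- 0/3 at 12.5 µg and 0/3 at 25 µg (Cycle 1 window): 0.065.
- 0/3 at 12.5 µg and 1/6 at 25 µg: 0.204. Here the first cohort's three participants have one DLT in Cycle 2, entered at the dose received, and the second cohort's three have none in Cycle 1.
- 1/3 at 12.5 µg and 0/3 at 25 µg: 0.375. The same DLT is entered at the starting dose.

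The first two are below the 0.25 limit, so the decision would not change. The third exceeds it, but nothing in the documents directs that entry.

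**The case against.** - **The SAP repeats Protocol 4.1.1.** The inconsistency starts inside the protocol, so SAP 4.8 had no departure from 4.1.1 to record. That is right about the origin. The SAP still adopts the version that the protocol's own Part 1 text contradicts, in a document that covers only Part 1.

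- **Each-cycle wording has a use.** Escalating an individual participant requires that no DLT has occurred (Protocol 4.1.2 and 6.4.1.1), so DLTs must be identifiable after Cycle 1. Part 2 maintenance also uses an each-cycle window. This makes Cycle 1 a likely intent rather than a certain one. It also means later events must not be dropped, which a separate table achieves.

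- **Misplacement is possible, not shown.** A DLT is an AE, and AE tables go by dose level. Table layouts are in the Output and Specification document, which was not available. That stands as a limit: whether the DLT summary also shows dose could not be checked. The text for that summary is nevertheless specific, and it says cohort.

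- **Four times is a ceiling.** Escalation needs at least 7 of 10 doses, no Grade 3 or higher AE, no DLT, no more than one Grade 2 CRS episode, and agreement of the investigator and Medical Monitor. This stands. The 800 µg upper dose in Protocol 6.1 equals 4 × 200 µg but proves nothing, since maintenance escalation in Part 2 could also reach it.

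- **The stakes are low.** No hypothesis is tested, no interim analysis or Part 2 follows, and the AE and exposure listings allow each event's cycle and dose to be recovered. This limits the consequence but does not settle which count is the planned one.

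**Conclusion.** The concern holds and should be fixed. As written, SAP 4.2.1 conflicts with the protocol's Part 1 definition. Combined with dose doubling and by-cohort counting, it can attribute a DLT at two or four times the starting dose to the starting-dose cohort. It also leaves the DLT-evaluable denominator undefined.

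In a cohort of three, one late event is the difference between 0/3 and 1/3. In a cohort of nine, it moves the observed proportion by 11.1 percentage points. These cases are hypothetical and assume that the participant escalated and that the DLT summary follows its by-cohort text.

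The practical effect is confined to the reported DLT counts in a synoptic report. Any effect on escalation decisions is secondary and was not demonstrated.

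**What to change.** - In SAP 4.2.1, state that for Part 1 the DLT-evaluable set (including the 70% rule) and the by-cohort DLT table use Cycle 1 Days 1–28.
- Tabulate events meeting DLT criteria in Cycles 2 and 3 separately, by dose received.
- State in the clinical study report which window the dose-escalation meetings used, and note that Protocol 4.1.1 differs from the Part 1 text.
- If the SAP will not be amended again, put the same definition in a footnote to the DLT table.

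The cost is one sentence or footnote, one small table and one statement in the report. No further participants or data are needed.

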# 4.2.2. Main analytical approach

Adverse events analyses including the analysis of AEs, SAEs, and other significant AEs will be based on GSK Core Data Standards. Summary tables will focus on treatment-emergent AEs (TEAE) only. Details on treatment-emergent AEs are provided in Section 6.2.2. AEs will be coded using the standard MedDRA and grouped by system organ class

(SOC). AEs will be graded by the investigator according to the NCI-CTCAE (version 5.0).

A summary of treatment-emergent adverse events by system organ class and preferred term and maximum grade will be produced. A summary of common non-serious TEAEs that occurred in strictly 10% of the participants or above will be provided (no rounding for the percentage will be used in terms of 10% threshold, e.g., events with 9.9% incidence rate should not be included in this table). A summary of common (>=10%) TEAEs by overall frequency. The summary of common non-serious AEs will be grouped by SOC and PT. A summary of common adverse events by overall frequency will be produced.

The summary will use the following algorithms for counting the participant:

**Preferred term row**: Participants experiencing the same AE preferred term several times with different grades will only be counted once with the maximum grade.

**Any event row**: Each participant with at least one adverse event will be counted only once at the maximum grade no matter how many events they have.

The date of the first occurrence of an AE will be used to indicate which dose level an AE should be reported in.

A study treatment-related AE is defined as an AE for which the investigator classifies the relationship to study treatment as "Yes". A worst-case scenario approach will be taken to handle missing relatedness data, i.e., the summary table will include events with the relationship to study treatment as 'Yes' or missing. Study treatment-related AEs will be summarized by SOC, PT, and maximum grade. An overall frequency summary of non-serious drug related treatment emergent adverse events will also be produced.

Serious TEAEs will be summarized by SOC, PT, and maximum grade, as well as a separate summary of serious TEAEs by SOC and PT (Number of subjects and Occurrences). A separate summary of serious fatal and non-fatal drug-related treatment emergent by overall frequency will be created for disclosure requirements to regulatory agencies, displayed by PT.

Additionally, a summary of the number of patients experiencing DLTs in each cohort will be provided for the dose escalation period. DLTs will be summarized according to GSK Oncology Data Standards.

All AEs (including SAEs and subject IDs for each individual AE) will be listed. A listing of reasons for considering as a serious adverse event will be generated.

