### Intra-patient dose escalation

In Part 1, participants are permitted to dose escalate between the 2-3 induction 5/2/5 q28d cycles based on discussion and agreement with Medical Monitor and the Investigator after reviewing available safety and laboratory data, and in line with the following safety and tolerability parameters:

- Investigator and MM must both consider that dose escalation is in the best interests of the participant
- Participant must have received at least 7 of the 10 doses in the prior cycle
- Participant must not have experienced:
  - $\circ$  Any Grade  $\geq$ 3 adverse event
  - $\circ$  Grade  $\geq$ 3 TLS
  - A DLT (which includes Grade 3 CRS, all non-hematologic Grade 3 events with a few exceptions as per Table 7)
  - More than 1 episode of Grade 2 CRS in the previous cycle
  - Evidence of ongoing immune related AEs during the observation period (sustained or intermittent Grade ≥2 fever ongoing after the first week of the observation period, in which infectious cause is ruled out).

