### 4. STATISTICAL ANALYSES

### 4.1. General Considerations

### 4.1.1. General Methodology

The Safety Analysis Set will be used for all study population, efficacy, and safety analyses, unless otherwise specified. AE and PK related tables, listings and figures will be summarized by dose level. Study population and efficacy tables and listings will be summarized by treatment sequence.

The DLT-evaluable Analysis Set will be used for assessment of dose-limiting toxicities.

Confidence intervals will use 95% confidence levels unless otherwise specified.

Unless otherwise specified, continuous data will be summarized using descriptive statistics: n, mean, standard deviation (std), median, minimum, and maximum. Categorical data will be summarized as the number and percentage of participants in each category.

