### 6.2.2.1. Treatment Emergent Flag for Adverse Events

Flag	Definition
Treatment Emergent	For AEs:  • Study Treatment Start Date ≤ AE Start Date ≤ Treatment Discontinuation Visit or Study Treatment Stop Date + 30 Days if TDV is missing  • AE Start Date is missing
	
 
For SAEs/AESIs:
 
Study Treatment Start Date ≤ AE Start Date or pre-existing (prior to exposure) AE Worsening Date ≤ Study Treatment Stop Date + 90 days or Start of Anti-Cancer Therapy, whichever occurs first
 
AE Start Date is missing
 

	Missing AE Start Date will be imputed following rules in Appendix 2 for determining Treatment Emergent AEs.

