# 6.2.6. Handling of Partial Dates

Element	Reporting Detail	
General	
 
Partial dates will be displayed as captured in participant listing displays.
 
However, where necessary, display macros may impute dates as temporary variables for sorting data in listings only. In addition, partial dates may be imputed for 'slotting' data to study phases or for specific analysis purposes as outlined below.
 
Imputed partial dates will not be used to derive study day, time to onset or duration (e.g., time to onset or duration of adverse events), or elapsed time variables (e.g., time since diagnosis). In addition, imputed dates are not used for deriving the last contact date in overall survival analysis dataset.
 
	
Adverse Events	
 
Partial dates for AE recorded in the CRF will be imputed using the following conventions:
 
Missing start day
 
If study intervention start date is missing (i.e., participant did not start study intervention), then set start date = 1st of month.
 
Else if study intervention start date is not missing:
 
If only a single dose level was given in the same month, then AE start date = 1st of the month or treatment start date (whichever is later).
 
If more than one dose level was given in the same month as the AE start date, then,
 
If AE end date contains a full date and AE end date is earlier than study intervention start date of the highest dose given that month, then set AE start date= 1st of month.
 
If AE end date contains a full date and AE end date is later than the study intervention start date of the highest dose given that month, then AE start date = study intervention start date of highest dose given that month.
 
If AE end date is missing, then set AE start date as the study intervention start date of the highest dose given that month.
 
Else set start date = 1st of month.
 
	
	Missing start day and month  If study intervention start date is missing (i.e., participant did not start study intervention), then set AE start date = January 1.  Else if study intervention start date is not missing:  If year of AE start date = year of study intervention start date, then	

	B 41 - 5 4 11	209809
Element	Reporting Detail	
		
 
If AE stop date contains a full date and AE stop date is earlier than study intervention start date, then set AE start date = January 1.
 

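### SAP 4.2.2 takes an AE's dose level from its first occurrence but its grade from its worst point, so one continuing AE that reaches Grade ≥3 after a dose doubling is tabulated as Grade ≥3 under the lower dose

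*SAP*

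**What the plan says.** SAP 4.1.1 fixes the columns of the safety tables: "AE and PK related tables, listings and figures will be summarized by dose level". It treats other displays differently: "Study population and efficacy tables and listings will be summarized by treatment sequence".

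SAP 4.2.2 then gives two rules. For the preferred-term row: "Participants experiencing the same AE preferred term several times with different grades will only be counted once with the maximum grade". For the column: "The date of the first occurrence of an AE will be used to indicate which dose level an AE should be reported in".

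The dose changes within a participant. Protocol 1.1 (Overall Design): "Within a cohort for an individual subject the dose may double for Cycle 2, and double again for Cycle 3 based on individual tolerability". Protocol 4.1.2 and 6.4.1.1 allow this only if the participant has had no Grade ≥3 AE and no DLT. Grade 1-2 events do not in general bar escalation, and one episode of Grade 2 CRS in the previous cycle is allowed. Protocol 4.1 and 6.4.1 also allow dose reduction.

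Two other SAP passages come close to the issue. Section 6.2.2.1 uses a date of worsening, "AE Start Date or pre-existing (prior to exposure) AE Worsening Date", but only to flag SAEs and AESIs that began before exposure as treatment-emergent. Section 6.2.6 covers an AE whose start day is unknown in a month with more than one dose level: "If AE end date is missing, then set AE start date as the study intervention start date of the highest dose given that month".

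**The concern.** When the dose is fixed, it does not matter that the dose level is read at onset and the grade at the worst point. When the dose can double twice in the same participant, it does. A low-grade AE that starts on the starting dose and becomes Grade ≥3 after a doubling keeps its starting-dose column and takes its later grade. The table then reports a Grade ≥3 event at a dose where the escalation criteria imply that the participant had none, and reports nothing for that term at the dose where it became severe.

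The pattern is plausible here. Protocol Table 5 describes cytokine-related symptoms and CRS in the solid-tumor study as dose dependent and Grade 1 or 2. Low-grade toxicity that worsens as the dose rises is what a dose-escalation table should show.

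Frequency and severity of AEs is the primary endpoint of Part 1. The rule governs the by-dose tables of treatment-emergent, treatment-related and serious AEs by maximum grade (SAP 4.2.2). Under SAP 4.1.1 it also reaches the AESI tables by maximum grade (SAP 4.3.2). The study has been terminated and the report is synoptic, so what is at stake is the dose-level safety record that remains.

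**Working it through.** The plan gives no figure to reproduce, so the check applies its rules to a case.

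**Inputs from the documents.** 28-day cycles; first cohort at 12.5 µg, doubling to 25 and 50 µg; cohorts of at least 3 (Protocol 4.1). Columns by dose level (SAP 4.1.1). Dose from first occurrence, grade from the maximum (SAP 4.2.2).

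**Assumed for illustration.** One participant receives 12.5 µg from day 1, 25 µg from day 29 and 50 µg from day 57. One preferred term, one record: Grade 1 on day 3, rising to Grade 3 on day 30. Each column's denominator is the number of participants treated at that dose.

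**Step 1: one continuing record.**
- SAP rule: dose = dose on day 3 = 12.5 µg; grade = max(1, 3) = 3. Result: Grade 3 under 12.5 µg, nothing under 25 µg.
- Grade by the dose in use: Grade 1 under 12.5 µg, Grade 3 under 25 µg.

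The record has one start date, so the result is the same whether participants are counted within or across columns.

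**Step 2: effect on the columns.** Suppose no one else has the event.

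| Column | By dose in use, Grade ≥3 | SAP rule, Grade ≥3 |
|---|---|---|
| 12.5 µg, cohort of 3 | 0/3 | 1/3 = 33.3% |
| 25 µg, same cohort | 1/3 = 33.3% | 0/3 |

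Pooling dilutes the change at the higher dose. With three cohorts of 3 starting at 12.5, 25 and 50 µg, all escalating twice, the numbers exposed at 12.5, 25, 50, 100 and 200 µg are 3, 6, 9, 6 and 3. Had the worsening come in Cycle 3, the 50 µg column would go from 1/9 = 11.1% to 0/9, while the 12.5 µg column would still go from 0/3 to 1/3.

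**Step 3: separate records of the same term** (Grade 1 on day 3, resolved; a new Grade 3 record on day 30).
- Counted once within each column: the second record has its own start date and falls under 25 µg. Nothing is misplaced.
- Counted once across columns: first occurrence is day 3 and maximum grade is 3, so the result is again Grade 3 under 12.5 µg.

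On the second reading only, suppose the term occurs at Grade 1-2 with probability q in each earlier cycle, independently. The share of Grade ≥3 events shown at a lower dose is q for those arising in Cycle 2 and 1 − (1 − q)² for those in Cycle 3.

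| q (assumed) | Cycle 2 | Cycle 3 |
|---|---|---|
| 0.20 | 20% | 1 − 0.80² = 36% |
| 0.35 | 35% | 1 − 0.65² = 57.75% |
| 0.50 | 50% | 1 − 0.50² = 75% |

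On the first reading all these shares are zero. They do not estimate how often a single record worsens.

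**Step 4: direction.** After escalation without reduction, the shift is from the higher dose to the lower. Take instead 12.5, 25, then 12.5 µg after a reduction. An AE that begins at Grade 2 on 25 µg and reaches Grade 3 back on 12.5 µg is shown under 25 µg, so the shift runs the other way.

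**Step 5: does another rule correct it?** No. The worsening date in SAP 6.2.2.1 sets a treatment-emergent flag, not a dose level. The highest-dose rule in SAP 6.2.6 applies to a missing start day, not to a rise in grade.

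**The case against.** The strongest reply is that SAP 4.2.2 contains two separate rules, one for counting participants and one for placing an AE. In a table by dose level, counting once within each column is a natural reading. The imputation in SAP 6.2.6 works on the individual AE's start date, and SAP 4.2.2 also plans an SAE summary of subjects and occurrences. SAP 1 leaves data handling conventions to the Output and Specification document, which is not available here. On that reading a recurrence in Cycle 2 is placed correctly. This stands for separate records, and the percentages in Step 3 fall with it.

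It does not rescue the single continuing record, unless the case report form opens a new record at each rise in grade. The documents do not say that it does.

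It is also fair that assignment by onset is prespecified and reproducible, that no hypothesis is tested in Part 1 (SAP 2), and that every AE is listed, so the individual cases remain visible.

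Three stronger readings are tempting, and the documents do not support them:
- That every Grade ≥3 AE in an escalated participant arose above the Cycle 1 dose, so that higher doses always look safer. Dose reductions (Protocol 4.1, 6.4.1) break both statements.
- That the by-dose gradient is known to be flattened by a given amount. That needs the count-once-across-columns reading and assumed event rates.
- That SAP 6.2.2.1 leaves a meaningful group of pre-exposure events without a dose level. Protocol 8.3.1 records events between consent and first dose as medical history, so this category should be nearly empty.

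**Conclusion.** Wrong as written, minor. SAP 4.2.2 pairs the dose at onset with the grade at worst. In a design with intra-patient doubling this puts a Grade ≥3 event under a dose at which the participant had none before escalating, if the AE is held as one continuing record. For separate records of one term the SAP is unclear rather than wrong.

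The actual size cannot be computed from the documents. One such participant in a cohort of 3 changes the starting-dose column from 0/3 to 1/3. The effect is zero for a participant whose dose never changes.

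A reader might infer that dose decisions were distorted. They were not: DLTs are summarized by cohort, the N-CRM works on DLTs, and the AE listing carries each event. The conclusion rests on the participant meeting the escalation criteria as written and on a rise in grade not opening a new AE record.

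**What to change.** In SAP 4.2.2, replace the first-occurrence rule with this: count each participant once per preferred term within each dose level, at the maximum grade reached while on that dose. Add an overall column in which each participant is counted once at the maximum grade across all doses. This also settles how separate records of one term are counted.

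The change needs the date of each rise in grade. The documents mention a worsening date only for SAEs and AESIs that began before exposure. If dates of grade change were not captured, also present the maximum-grade AE tables by treatment sequence, as SAP 4.1.1 already does for study population and efficacy. That needs no new data.

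The cost is two or three sentences and a little more derivation work, for a Part 1 planned at about 22 participants. A participant may then appear in more than one dose column, so the columns will not add up to the overall column; a footnote should say so.
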